**FIGURE 14.2-1.13 Mean height velocity over time by completer, means  $\pm$  95% CI (FAS)**

**FIGURE 14.2-1.13.1 Mean height velocity over time by completer and sex, means  $\pm$  95% CI (FAS)**

**FIGURE 14.2-1.14 Mean HV SDS (cross-sectional) over time by completer, means  $\pm$  95% CI (FAS)**

**FIGURE 14.2-1.14.1 Mean HV SDS (cross-sectional) over time for patients with and without positive anti-rhGH antibodies, means  $\pm$  95% CI (FAS)**

**FIGURE 14.2-1.15 Mean HV SDS (peak-centered) over time by completer, means  $\pm$  95% CI (FAS)**

**FIGURE 14.2-1.15.1 Mean HV SDS (peak-centered) over time for patients with and without positive anti-rhGH antibodies, means  $\pm$  95% CI (FAS)**

**FIGURE 14.2-2.19 Mean IGF-1 serum levels over time, means  $\pm$  95% CI (FAS)**

**FIGURE 14.2-2.19.1 Mean IGF-1 serum levels over time by sex, means  $\pm$  95% CI (FAS)**

**FIGURE 14.2-2.20 Mean IGFBP-3 serum levels over time, means  $\pm$  95% CI (FAS)**

**FIGURE 14.2-2.20.1 Mean IGFBP-3 serum levels over time by sex, means  $\pm$  95% CI (FAS)**

**FIGURE 14.2-2.21 Mean IGF-1 SDS serum levels over time, means  $\pm$  95% CI (FAS)**

**FIGURE 14.2-2.22 Mean IGFBP-3 SDS serum levels over time, means  $\pm$  95% CI (FAS)**

**5.4 Safety Tables including shells**

**TABLE 14.3-1.1 GENERAL SUMMARY OF ADVERSE EVENTS (SAF)**

		Number of patients (%) (N=277)	Number of adverse events (%)
Any adverse events	XXX	(XX.X%)	XXX
Relationship to study drug			(XX.X%)
Not suspected	XXX	(XX.X%)	XXX
Suspected	XXX	(XX.X%)	XXX
Missing	XXX	(XX.X%)	XXX
Intensity			(XX.X%)
Mild	XXX	(XX.X%)	XXX
Moderate	XXX	(XX.X%)	XXX
Severe	XXX	(XX.X%)	XXX
Missing	XXX	(XX.X%)	XXX
Serious adverse event			(XX.X%)
No	XXX	(XX.X%)	XXX
Yes	XXX	(XX.X%)	XXX
Missing	XXX	(XX.X%)	XXX
Outcome			(XX.X%)
Resolved	XXX	(XX.X%)	XXX
Ongoing	XXX	(XX.X%)	XXX
Missing	XXX	(XX.X%)	XXX
Action taken			(XX.X%)
Nothing	XXX	(XX.X%)	XXX
Study drug dosage adjusted/temporarily interrupted	XXX	(XX.X%)	XXX
Study drug permanently discontinued due to this AE	XXX	(XX.X%)	XXX
Concomitant medication given	XXX	(XX.X%)	XXX
Non-drug therapy given	XXX	(XX.X%)	XXX
Hospitalization/prolonged hospitalization	XXX	(XX.X%)	XXX
Missing	XXX	(XX.X%)	XXX

No AEs (including SAEs) that started prior to start of treatment are included.

**TABLE 14.3-1.2 INCIDENCE OF ADVERSE EVENTS BY SYSTEM ORGAN CLASS, PREFERRED TERM, AND INTENSITY, ALL ADVERSE EVENTS (SAF)****TABLE 14.3-1.2.1 INCIDENCE OF ADVERSE EVENTS FOR OVERWEIGHT\* PATIENTS AT BASELINE BY SYSTEM ORGAN CLASS, PREFERRED TERM, AND INTENSITY, ALL ADVERSE EVENTS (SAF)**

Defined by international cut off points for BMI for overweight by sex and age at baseline. The cut-off point is defined by the percentile that passes through BMI at 25 kg/m^2 at age 18.. Programming note: Same table shell as Table 14.3-1.2 will be used.

**TABLE 14.3-1.3 INCIDENCE OF ADVERSE EVENTS BY SYSTEM ORGAN CLASS, PREFERRED TERM, AND INTENSITY, DRUG-RELATED ADVERSE EVENTS (SAF)****TABLE 14.3-1.4 INCIDENCE OF SERIOUS ADVERSE EVENTS BY SYSTEM ORGAN CLASS, PREFERRED TERM, AND INTENSITY (SAF)****TABLE 14.3-1.5 INCIDENCE OF DRUG-RELATED SERIOUS ADVERSE EVENTS BY SYSTEM ORGAN CLASS, PREFERRED TERM, AND INTENSITY (SAF)****TABLE 14.3-1.6 INCIDENCE OF NON-SERIOUS ADVERSE EVENTS BY SYSTEM ORGAN CLASS, PREFERRED TERM, AND INTENSITY (SAF)**

Novartis MedDRA version System Organ Class Preferred Term	Intensity				Total number of patients	Patients per patient years#
	Mild	Moderate	Severe	Missing		
Blood and lymphatic system disorders						
Any AE	XX (XX.X%)	XX (XX.X%)	XX (XX.X%)	XX (XX.X%)	XX (XX.X%)	X.XXX
Anaemia	XX (XX.X%)	XX (XX.X%)	XX (XX.X%)	XX (XX.X%)	XX (XX.X%)	X.XXX
Eosinophilia	XX (XX.X%)	XX (XX.X%)	XX (XX.X%)	XX (XX.X%)	XX (XX.X%)	X.XXX
Leukopenia	XX (XX.X%)	XX (XX.X%)	XX (XX.X%)	XX (XX.X%)	XX (XX.X%)	X.XXX
Lymphadenitis	XX (XX.X%)	XX (XX.X%)	XX (XX.X%)	XX (XX.X%)	XX (XX.X%)	X.XXX
Lymphadenopathy	XX (XX.X%)	XX (XX.X%)	XX (XX.X%)	XX (XX.X%)	XX (XX.X%)	X.XXX
Neutropenia	XX (XX.X%)	XX (XX.X%)	XX (XX.X%)	XX (XX.X%)	XX (XX.X%)	X.XXX
Splenomegaly	XX (XX.X%)	XX (XX.X%)	XX (XX.X%)	XX (XX.X%)	XX (XX.X%)	X.XXX

Novartis MedDRA version System Organ Class Preferred Term	Intensity				Total number of patients	Patients per patient years#
	Mild	Moderate	Severe	Missing		
Thrombocytopenia	XX (XX.X%)	XX (XX.X%)	XX (XX.X%)	XX (XX.X%)	XX (XX.X%)	X.XXX
Thrombocytosis	XX (XX.X%)	XX (XX.X%)	XX (XX.X%)	XX (XX.X%)	XX (XX.X%)	X.XXX
Cardiac disorders						
Any AE	XX (XX.X%)	XX (XX.X%)	XX (XX.X%)	XX (XX.X%)	XX (XX.X%)	X.XXX
...	XX (XX.X%)	XX (XX.X%)	XX (XX.X%)	XX (XX.X%)	XX (XX.X%)	X.XXX

No AEs (including SAEs) that started prior to start of treatment are included.

# Patient years = XXX.XXX

Patient years are calculated as years of exposure (i.e. total sum of the number of years that each patient was treated).

**TABLE 14.3-1.7 OCCURRENCE OF ADVERSE EVENTS BY SYSTEM ORGAN CLASS, PREFERRED TERM, AND INTENSITY, ALL ADVERSE EVENTS (SAF)**

**TABLE 14.3-1.8 OCCURRENCE OF ADVERSE EVENTS BY SYSTEM ORGAN CLASS, PREFERRED TERM, AND INTENSITY, DRUG-RELATED ADVERSE EVENTS (SAF)**

**TABLE 14.3-1.9 OCCURRENCE OF SERIOUS ADVERSE EVENTS BY SYSTEM ORGAN CLASS, PREFERRED TERM, AND INTENSITY (SAF)**

**TABLE 14.3-1.10 OCCURRENCE OF DRUG-RELATED SERIOUS ADVERSE EVENTS BY SYSTEM ORGAN CLASS, PREFERRED TERM, AND INTENSITY (SAF)**

**TABLE 14.3-1.11 OCCURRENCE OF NON-SERIOUS ADVERSE EVENTS BY SYSTEM ORGAN CLASS, PREFERRED TERM, AND INTENSITY (SAF)**

SOC	Preferred term	Intensity				Missing	Total	Events per Patient Year
		Mild	Moderate	Severe				
SOC1	ANY	XX	XX	XX	XX	XX	XX	X.XXX
	Preferred Term 1	XX	XX	XX	XX	XX	XX	X.XXX
	Preferred Term 2	XX	XX	XX	XX	XX	XX	X.XXX
	Preferred Term X	XX	XX	XX	XX	XX	XX	X.XXX
	...	...	...	...	...	...	...	...
	...	...	...	...	...	...	...	...
SOC2	ANY	XX	XX	XX	XX	XX	XX	X.XXX
	Preferred Term 1	XX	XX	XX	XX	XX	XX	X.XXX
	Preferred Term 2	XX	XX	XX	XX	XX	XX	X.XXX
	Preferred Term X	XX	XX	XX	XX	XX	XX	X.XXX
	...	...	...	...	...	...	...	...
	...	...	...	...	...	...	...	...

No AEs (including SAEs) that started prior to start of treatment are included.

# Patient years = XXX.XXX

Patient years are calculated as years of exposure (i.e. total sum of the number of years that each patient was treated).

**TABLE 14.3-1.12 INCIDENCE OF ADVERSE EVENTS BY SYSTEM ORGAN CLASS, PREFERRED TERM, AND OUTCOME, ALL ADVERSE EVENTS (SAF)**

**TABLE 14.3-1.13 INCIDENCE OF ADVERSE EVENTS BY SYSTEM ORGAN CLASS, PREFERRED TERM, AND OUTCOME, DRUG-RELATED ADVERSE EVENTS (SAF)**

**TABLE 14.3-1.14 INCIDENCE OF SERIOUS ADVERSE EVENTS BY SYSTEM ORGAN CLASS, PREFERRED TERM, AND OUTCOME (SAF)**

**TABLE 14.3-1.15 INCIDENCE OF DRUG-RELATED SERIOUS ADVERSE EVENTS BY SYSTEM ORGAN CLASS, PREFERRED TERM, AND OUTCOME (SAF)**

Novartis MedDRA version System Organ Class Preferred Term	Outcome				Total number of patients	Patients per patient years#
	Resolved	Ongoing	Fatal	Missing		
Blood and lymphatic system disorders						
Any AE	XX (XX.X%)	X.XXX				
Anaemia	XX (XX.X%)	X.XXX				
Eosinophilia	XX (XX.X%)	X.XXX				
Leukopenia	XX (XX.X%)	X.XXX				
Lymphadenitis	XX (XX.X%)	X.XXX				
Lymphadenopathy	XX (XX.X%)	X.XXX				
Neutropenia	XX (XX.X%)	X.XXX				
Splenomegaly	XX (XX.X%)	X.XXX				
Thrombocytopenia	XX (XX.X%)	X.XXX				
Thrombocytosis	XX (XX.X%)	X.XXX				
Cardiac disorders						
Any AE	XX (XX.X%)	X.XXX				
...	XX (XX.X%)	X.XXX				

No AEs (including SAEs) that started prior to start of treatment are included.

# Patient years = XXX.XXX

Patient years are calculated as years of exposure (i.e. total sum of the number of years that each patient was treated).

**TABLE 14.3-1.16 OCCURRENCE OF ADVERSE EVENTS BY SYSTEM ORGAN CLASS, PREFERRED TERM, AND OUTCOME, ALL ADVERSE EVENTS (SAF)**

**TABLE 14.3-1.17 OCCURRENCE OF ADVERSE EVENTS BY SYSTEM ORGAN CLASS, PREFERRED TERM, AND OUTCOME, DRUG-RELATED ADVERSE EVENTS (SAF)**

**TABLE 14.3-1.18 OCCURRENCE OF SERIOUS ADVERSE EVENTS BY SYSTEM ORGAN CLASS, PREFERRED TERM, AND OUTCOME (SAF)**

**TABLE 14.3-1.19 OCCURRENCE OF DRUG-RELATED SERIOUS ADVERSE EVENTS BY SYSTEM ORGAN CLASS, PREFERRED TERM, AND OUTCOME (SAF)**

Novartis MedDRA 19.1 System organ class Preferred Term	Outcome					Events per patient year#
	Resolved	Ongoing	Fatal	Missing	Total	
	XXX	XXX	XXX	XXX	XXX	
Blood and lymphatic system disorders						X.XXX
ANY	XXX	XXX	XXX	XXX	XXX	X.XXX
Anaemia	XXX	XXX	XXX	XXX	XXX	X.XXX
Eosinophilia	XXX	XXX	XXX	XXX	XXX	X.XXX
Leukopenia	XXX	XXX	XXX	XXX	XXX	X.XXX
Lymphadenitis	XXX	XXX	XXX	XXX	XXX	X.XXX
Lymphadenopathy	XXX	XXX	XXX	XXX	XXX	X.XXX
Neutropenia	XXX	XXX	XXX	XXX	XXX	X.XXX
Splenomegaly	XXX	XXX	XXX	XXX	XXX	X.XXX
Thrombocytopenia	XXX	XXX	XXX	XXX	XXX	X.XXX
Thrombocytosis	XXX	XXX	XXX	XXX	XXX	X.XXX
Cardiac disorders	XXX	XXX	XXX	XXX	XXX	X.XXX
ANY	XXX	XXX	XXX	XXX	XXX	X.XXX
...						

No AEs (including SAEs) that started prior to start of treatment are included.

# Patient years = XXX.XXX

Patient years are calculated as years of exposure (i.e. total sum of the number of years that each patient was treated).

**TABLE 14.3-1.20 INCIDENCE OF ADVERSE EVENTS BY SYSTEM ORGAN CLASS, PREFERRED TERM, AND ACTION TAKEN, ALL ADVERSE EVENTS (SAF)**

**TABLE 14.3-1.21 INCIDENCE OF ADVERSE EVENTS BY SYSTEM ORGAN CLASS, PREFERRED TERM, AND ACTION TAKEN, DRUG-RELATED ADVERSE EVENTS (SAF)**

**TABLE 14.3-1.22 INCIDENCE OF SERIOUS ADVERSE EVENTS BY SYSTEM ORGAN CLASS, PREFERRED TERM, AND ACTION TAKEN (SAF)**

**TABLE 14.3-1.23 INCIDENCE OF DRUG-RELATED SERIOUS ADVERSE EVENTS BY SYSTEM ORGAN CLASS, PREFERRED TERM, AND ACTION TAKEN (SAF)**

Novartis MedDRA 19.1 System Organ Class Preferred Term	Nothing interrupted	Action taken								Patients per patient years#
		Study drug dosage adjusted /tempo- rarily inter- rupted	Study drug perma- nently disc- ontinued	Conco- mitant medi- cation given	Non-drug therapy given	Hospital- ization/ prolonged hospital- ization	Missing			
Blood and lymphatic system disorders										
Any AE	XX (XX.X%)	XX (XX.X%)	XX (XX.X%)	XX (XX.X%)	XX (XX.X%)	XX (XX.X%)	XX (XX.X%)	XX (XX.X%)	XX (XX.X%)	X.XXX
Anaemia	XX (XX.X%)	XX (XX.X%)	XX (XX.X%)	XX (XX.X%)	XX (XX.X%)	XX (XX.X%)	XX (XX.X%)	XX (XX.X%)	XX (XX.X%)	X.XXX
Eosinophilia	XX (XX.X%)	XX (XX.X%)	XX (XX.X%)	XX (XX.X%)	XX (XX.X%)	XX (XX.X%)	XX (XX.X%)	XX (XX.X%)	XX (XX.X%)	X.XXX
Leukopenia	XX (XX.X%)	XX (XX.X%)	XX (XX.X%)	XX (XX.X%)	XX (XX.X%)	XX (XX.X%)	XX (XX.X%)	XX (XX.X%)	XX (XX.X%)	X.XXX
Lymphadenitis	XX (XX.X%)	XX (XX.X%)	XX (XX.X%)	XX (XX.X%)	XX (XX.X%)	XX (XX.X%)	XX (XX.X%)	XX (XX.X%)	XX (XX.X%)	X.XXX
Lymphadenopathy	XX (XX.X%)	XX (XX.X%)	XX (XX.X%)	XX (XX.X%)	XX (XX.X%)	XX (XX.X%)	XX (XX.X%)	XX (XX.X%)	XX (XX.X%)	X.XXX
Neutropenia	XX (XX.X%)	XX (XX.X%)	XX (XX.X%)	XX (XX.X%)	XX (XX.X%)	XX (XX.X%)	XX (XX.X%)	XX (XX.X%)	XX (XX.X%)	X.XXX
...										

No AEs (including SAEs) that started prior to start of treatment are included.

# Patient years = XXX.XXX

Patient years are calculated as years of exposure (i.e. total sum of the number of years that each patient was treated).

**TABLE 14.3-1.24 OCCURRENCE OF ADVERSE EVENTS BY SYSTEM ORGAN CLASS, PREFERRED TERM, AND ACTION TAKEN, ALL ADVERSE EVENTS (SAF)**

**TABLE 14.3-1.25 OCCURRENCE OF ADVERSE EVENTS BY SYSTEM ORGAN CLASS, PREFERRED TERM, AND ACTION TAKEN, DRUG-RELATED ADVERSE EVENTS (SAF)**

**TABLE 14.3-1.26 OCCURRENCE OF SERIOUS ADVERSE EVENTS BY SYSTEM ORGAN CLASS, PREFERRED TERM, AND ACTION TAKEN (SAF)**

**TABLE 14.3-1.27 OCCURRENCE OF DRUG-RELATED SERIOUS ADVERSE EVENTS BY SYSTEM ORGAN CLASS, PREFERRED TERM, AND ACTION TAKEN (SAF)**

Novartis MedDRA 19.1	System organ class Preferred Term	Action taken						Events per patient year#	
		Study drug dosage adjusted /tempo- rarily	Study drug perma- nently disc- ontinued	Conco- mitant medi- cation given	Hospital- ization/ prolonge d	Non-drug therapy given	Hospital- ization		
Blood and lymphatic system disorders									
ANY		XXX	XXX	XXX	XXX	XXX	XXX	XXX	X.XXX
Anaemia		XXX	XXX	XXX	XXX	XXX	XXX	XXX	X.XXX
Eosinophilia		XXX	XXX	XXX	XXX	XXX	XXX	XXX	X.XXX
Leukopenia		XXX	XXX	XXX	XXX	XXX	XXX	XXX	X.XXX
Lymphadenitis		XXX	XXX	XXX	XXX	XXX	XXX	XXX	X.XXX
Lymphadenopathy		XXX	XXX	XXX	XXX	XXX	XXX	XXX	X.XXX
Neutropenia		XXX	XXX	XXX	XXX	XXX	XXX	XXX	X.XXX
Splenomegaly		XXX	XXX	XXX	XXX	XXX	XXX	XXX	X.XXX
Thrombocytopenia		XXX	XXX	XXX	XXX	XXX	XXX	XXX	X.XXX
Thrombocytosis		XXX	XXX	XXX	XXX	XXX	XXX	XXX	X.XXX
Cardiac disorders		XXX	XXX	XXX	XXX	XXX	XXX	XXX	X.XXX
ANY		XXX	XXX	XXX	XXX	XXX	XXX	XXX	X.XXX
Bradycardia		XXX	XXX	XXX	XXX	XXX	XXX	XXX	X.XXX
...		XXX	XXX	XXX	XXX	XXX	XXX	XXX	X.XXX

No AEs (including SAEs) that started prior to start of treatment are included.

# Patient years = XXX.XXX

Patient years are calculated as years of exposure (i.e. total sum of the number of years that each patient was treated).

**TABLE 14.3-2.1 CONVERSION FACTORS FOR LABORATORY PARAMETERS**

	Parameter	Unit measured	Conversion factor	Unit derived
Hematology	Hematocrit	% / 100		Value
	Hemoglobin	g/dl	10	g/l
	MCHC	g/dl	10	g/l
Blood chemistry	Total protein	g/dl	10	g/l
	Creatinine	mg/dl	XX.X	umol/l
	Total bilirubin	mg/dl	XX.X	umol/l
	Urea	mg/dl	X.XXX	mmol/l
...	...	...	...	...

**TABLE 14.3-2.2 SUMMARY OF HEMATOLOGY DATA (SAF)**

**TABLE 14.3-2.3 SUMMARY OF BLOOD CHEMISTRY (SAF)**

TABLE 14.3-2.4 SUMMARY OF CARBOHYDRATE METABOLISM INCL. OGTT DATA (SAF)

**TABLE 14.3-2.5 SUMMARY OF ABSOLUTE CHANGES FROM BASELINE OF CARBOHYDRATE METABOLISM INCL. OGTT DATA (SAF)**

TABLE 14.3-2.6 SUMMARY OF RELATIVE CHANGES FROM BASELINE OF CARBOHYDRATE METABOLISM INCL. OGTT DATA (SAF)

**TABLES 14.3-2.7 SHIFT TABLES FOR CARBOHYDRATE METABOLISM (SAF)**

**TABLE 14.3-2.7.1 SHIFT TABLE FOR HbA1C (SAF)**

**TABLE 14.3-2.7.2 SHIFT TABLE FOR FASTING GLUCOSE (SAF)**

**TABLE 14.3-2.7.3 SHIFT TABLE FOR FASTING INSULIN (SAF)**

Comparison (Baseline vs Compared)	Base Visit	Low	Normal	High	Missing	Total
V01 vs V03	Low	XX ( XX.X%)	XX ( XX.X%)	XX ( XX.X%)	XX	XX ( XX.X%)
	Normal	XX ( XX.X%)	XX ( XX.X%)	XX ( XX.X%)	XX	XX ( XX.X%)
	High	XX ( XX.X%)	XX ( XX.X%)	XX ( XX.X%)	XX	XX ( XX.X%)
	Missing	XX	XX	XX	XX	XX
	Total	XX ( XX.X%)	XX ( XX.X%)	XX ( XX.X%)	XX	XXX (100.0%)
V01 vs V05	Low	XX ( XX.X%)	XX ( XX.X%)	XX ( XX.X%)	XX	XX ( XX.X%)
	Normal	XX ( XX.X%)	XX ( XX.X%)	XX ( XX.X%)	XX	XX ( XX.X%)
	High	XX ( XX.X%)	XX ( XX.X%)	XX ( XX.X%)	XX	XX ( XX.X%)
	Missing	XX	XX	XX	XX	XX
	Total	XX ( XX.X%)	XX ( XX.X%)	XX ( XX.X%)	XX	XXX (100.0%)
V... vs V..	Low	XX ( XX.X%)	XX ( XX.X%)	XX ( XX.X%)	XX	XX ( XX.X%)
	Normal	XX ( XX.X%)	XX ( XX.X%)	XX ( XX.X%)	XX	XX ( XX.X%)
	High	XX ( XX.X%)	XX ( XX.X%)	XX ( XX.X%)	XX	XX ( XX.X%)
	Missing	XX	XX	XX	XX	XX
	Total	XX ( XX.X%)	XX ( XX.X%)	XX ( XX.X%)	XX	XXX (100.0%)

**TABLE 14.3-2.8 SUMMARY OF HOMA AND QUICKI SCORES (SAF)**

**TABLE 14.3-2.9 SUMMARY OF ABSOLUTE CHANGES FROM BASELINE OF HOMA AND QUICKI SCORES (SAF)**

**TABLE 14.3-2.10 SUMMARY OF RELATIVE CHANGES FROM BASELINE OF HOMA AND QUICKI SCORES (SAF)**

**TABLE 14.3-2.11 SUMMARY OF THYROID PANEL DATA (SAF)**

**TABLES 14.3-2.12 SHIFT TABLES FOR THYROID PANEL DATA (SAF)**

**TABLE 14.3-2.12.1 SHIFT TABLE FOR FREE THYROXINE (T4) (SAF)**

**TABLE 14.3-2.12.2 SHIFT TABLE FOR THYROID STIMULATING HORMONE (TSH)  
(SAF)**

Comparison (Baseline vs Compared)	Base Visit	Low	Normal	High	Missing	Total
V01 vs V03	Low	XX ( XX.X%)	XX ( XX.X%)	XX ( XX.X%)	XX	XX ( XX.X%)
	Normal	XX ( XX.X%)	XX ( XX.X%)	XX ( XX.X%)	XX	XX ( XX.X%)
	High	XX ( XX.X%)	XX ( XX.X%)	XX ( XX.X%)	XX	XX ( XX.X%)
	Missing	XX	XX	XX	XX	XX
	Total	XX ( XX.X%)	XX ( XX.X%)	XX ( XX.X%)	XX	XXX (100.0%)
V01 vs V05	Low	XX ( XX.X%)	XX ( XX.X%)	XX ( XX.X%)	XX	XX ( XX.X%)
	Normal	XX ( XX.X%)	XX ( XX.X%)	XX ( XX.X%)	XX	XX ( XX.X%)
	High	XX ( XX.X%)	XX ( XX.X%)	XX ( XX.X%)	XX	XX ( XX.X%)
	Missing	XX	XX	XX	XX	XX
	Total	XX ( XX.X%)	XX ( XX.X%)	XX ( XX.X%)	XX	XXX (100.0%)
V01 vs V..	Low	XX ( XX.X%)	XX ( XX.X%)	XX ( XX.X%)	XX	XX ( XX.X%)
	Normal	XX ( XX.X%)	XX ( XX.X%)	XX ( XX.X%)	XX	XX ( XX.X%)
	High	XX ( XX.X%)	XX ( XX.X%)	XX ( XX.X%)	XX	XX ( XX.X%)
	Missing	XX	XX	XX	XX	XX
	Total	XX ( XX.X%)	XX ( XX.X%)	XX ( XX.X%)	XX	XXX (100.0%)

**TABLE 14.3-2.13 SUMMARY OF URINALYSIS DATA (SAF)**

Parameter (unit)	Visit	N	N miss	Mean	SD	Min	Q1	Media n	Q3	Max										
Parameter 1 (unit1)	V01	XX	XX	XXX.	XX.X	XXX	XXX.	XXX.	XXX.	XXX										
				XX	X		XX	XX	XX	XX										
	V03	XX	XX	XXX.	XX.X	XXX	XXX.	XXX.	XXX.	XXX										
				XX	X		XX	XX	XX	XX										
	V05	XX	XX	XXX.	XX.X	XXX	XXX.	XXX.	XXX.	XXX										
				XX	X		XX	XX	XX	XX										
	...																			
	Parameter 2 (unit2)	V01	XX	XX	X.XX	X.XX	X.XX	X.XX	X.XX	X.XX										
	V03	XX	XX	X.XX	X.XX	X.XX	X.XX	X.XX	X.XX	X.XX										
	V05	XX	XX	X.XX	X.XX	X.XX	X.XX	X.XX	X.XX	X.XX										
...																				
...																				
...																				
...																				

**TABLES 14.3-2.14 SHIFT TABLES FOR URINALYSIS DATA (SAF)****TABLE 14.3-2.14.1 SHIFT TABLE FOR PROTEIN (SAF)****TABLE 14.3-2.14.2 SHIFT TABLE FOR GLUCOSE (SAF)****TABLE 14.3-2.14.3 SHIFT TABLE FOR KETONES (SAF)**

Comparison (Baseline vs Compared)	Base Visit	Negative	+	++	+	++	Missing	Total
	Total	XXX (XX.X%)	XXX (XX.X%)	XXX (XX.X%)	XXX (XX.X%)	XXX (XX.X%)	XX	XXX (XX.X%)

**TABLE 14.3-3.1 SUMMARY OF VITAL SIGNS (SAF)**

**TABLE 14.3-3.2 SUMMARY OF PHYSICAL EXAMINATION (SAF)**

Body System	Visit	Total	Missing	N	Significant findings Number of patients (%)	
					Yes	No
General appearance	SCR	XXX	XXX	XXX	XX (XX.X%)	XX (XX.X%)
	V01	XXX	XXX	XXX	XX (XX.X%)	XX (XX.X%)
	V02	XXX	XXX	XXX	XX (XX.X%)	XX (XX.X%)
	V03	XXX	XXX	XXX	XX (XX.X%)	XX (XX.X%)
	V04	XXX	XXX	XXX	XX (XX.X%)	XX (XX.X%)
	V05	XXX	XXX	XXX	XX (XX.X%)	XX (XX.X%)
	V06	XXX	XXX	XXX	XX (XX.X%)	XX (XX.X%)
	V07	XXX	XXX	XXX	XX (XX.X%)	XX (XX.X%)
	V08	XXX	XXX	XXX	XX (XX.X%)	XX (XX.X%)
Head	...	XXX	XXX	XXX	XX (XX.X%)	XX (XX.X%)
	SCR	XXX	XXX	XXX	XX (XX.X%)	XX (XX.X%)
	V01	XXX	XXX	XXX	XX (XX.X%)	XX (XX.X%)
	V02	XXX	XXX	XXX	XX (XX.X%)	XX (XX.X%)
	V03	XXX	XXX	XXX	XX (XX.X%)	XX (XX.X%)
	V04	XXX	XXX	XXX	XX (XX.X%)	XX (XX.X%)
	V05	XXX	XXX	XXX	XX (XX.X%)	XX (XX.X%)
	V06	XXX	XXX	XXX	XX (XX.X%)	XX (XX.X%)
	V07	XXX	XXX	XXX	XX (XX.X%)	XX (XX.X%)
	V08	XXX	XXX	XXX	XX (XX.X%)	XX (XX.X%)
...	...	XXX	XXX	XXX	XX (XX.X%)	XX (XX.X%)

**TABLE 14.3-3.3 SHIFT TABLE FOR PHYSICAL EXAMINATION BY BODY SYSTEM (SAF)**

Body System	Comparison (Baseline vs Compared)	Base Visit	Normal	Abnormal	Missing	Total
General appearance	V01 vs V02	Normal	XX (XX.X%)	XX (XX.X%)	XX	XX (XX.X%)
		Abnormal	XX (XX.X%)	XX (XX.X%)	XX	XX (XX.X%)
		Missing	XX	XX	XX	XX
		Total	XX (XX.X%)	XX (XX.X%)	XX	XXX (100.0%)
	V01 vs V03	Normal	XX (XX.X%)	XX (XX.X%)	XX	XX (XX.X%)
		Abnormal	XX (XX.X%)	XX (XX.X%)	XX	XX (XX.X%)
		Missing	XX	XX	XX	XX
		Total	XX (XX.X%)	XX (XX.X%)	XX	XXX (100.0%)
	...	...	...	...	...	...

Body System	Comparison (Baseline vs Compared)	Base Visit	Normal		Abnormal		Missing	Total
			Normal	Abnormal	Normal	Abnormal		
Head	V01 vs V02	Normal	XX ( XX.X%)	XX ( XX.X%)	XX	XX ( XX.X%)		XXX (100.0%)
		Abnormal	XX ( XX.X%)	XX ( XX.X%)	XX	XX ( XX.X%)		
		Missing	XX	XX	XX	XX		
		Total	XX ( XX.X%)	XX ( XX.X%)	XX	XX		
	V01 vs V03	Normal	XX ( XX.X%)	XX ( XX.X%)	XX	XX ( XX.X%)		XXX (100.0%)
		Abnormal	XX ( XX.X%)	XX ( XX.X%)	XX	XX ( XX.X%)		
		Missing	XX	XX	XX	XX		
		Total	XX ( XX.X%)	XX ( XX.X%)	XX	XX		

**TABLE 14.3-3.4 SUMMARY OF BODY WEIGHT (SAF)**

**TABLE 14.3-3.5 SUMMARY OF BMI (SAF)**

**TABLE 14.3-3.6 SUMMARY OF BMI SDS (SAF)**

	Visit	N	N miss	Mean	SD	Min	Q1	Median	Q3	Max
BMI SDS	01	XX	XX	XX.X	X.X	XX.X	XX.X	XX.X	XX.X	XX.X
	02	XX	XX	XX.X	X.X	XX.X	XX.X	XX.X	XX.X	XX.X
	03	XX	XX	XX.X	X.X	XX.X	XX.X	XX.X	XX.X	XX.X
	...	XX	XX	XX.X	X.X	XX.X	XX.X	XX.X	XX.X	XX.X

**TABLE 14.3-3.7 SUMMARY OF PATIENTS WITH LABORATORY PARAMETERS FULLFILING THE DEFINITION OF DIABETES MELLITUS (DM) (SAF)**

	Total	Number of patients with DM (%)	Number of patients without DM finding (%)
Female	XXX	XX (XX.X%)	XX (XX.X%)
Male	XXX	XX (XX.X%)	XX (XX.X%)
Total	XXX	XX (XX.X%)	XX (XX.X%)

DM is defined as fulfilment of one of the following criteria:

1. FPG  $\geq 126$  mg/dl ( $\geq 7.0$  mmol/l) during safety lab assessment or as -10min value of OGTT
2. 2-h plasma glucose  $\geq 200$  mg/dl ( $\geq 11.1$  mmol/l) during OGTT
3. HbA1C  $\geq 6.5\%$

Patients not fulfilling at least one criteria on at least one visit are considered as patients without DM finding

**TABLE 14.3-3.7.1 SUMMARY OF OVERWEIGHT\* PATIENTS AT BASELINE WITH LABORATORY PARAMETERS FULLFILING THE DEFINITION OF DIABETES MELLITUS (DM) (SAF)**

Sex	Total	Number of patients with DM (%)	Number of patients without DM finding (%)
Female	XXX	XX (XX.X%)	XX (XX.X%)
Male	XXX	XX (XX.X%)	XX (XX.X%)
Total	XXX	XX (XX.X%)	XX (XX.X%)

\* Defined by international cut off points for BMI for overweight by sex and age at baseline. The cut-off point is defined by the percentile that passes through BMI at 25 kg/m^2 at age 18.

DM is defined as fulfilment of one of the following criteria:

1. FPG  $\geq 126$  mg/dl ( $\geq 7.0$  mmol/l) during OGTT or safety lab assessment
2. 2-h plasma glucose  $\geq 200$  mg/dl ( $\geq 11.1$  mmol/l) during OGTT
3. HbA1C  $\geq 6.5\%$

Patients not fulfilling at least one criteria on at least one visit are considered as patients without DM finding

**TABLE 14.3-3.8 SUMMARY OF PATIENTS WITH LABORATORY PARAMETERS FULLFILING THE DEFINITION OF IMPAIRED GLUCOSE TOLERANCE (IGT) (SAF)**

	Total	Number of patients with IGT (%)	Number of patients without IGT finding (%)
Female	XXX	XX (XX.X%)	XX (XX.X%)
Male	XXX	XX (XX.X%)	XX (XX.X%)
Total	XXX	XX (XX.X%)	XX (XX.X%)

IGT is defined as fulfilment of all of the following criteria:

1. FPG < 126 mg/dl (<7.0 mmol/l) during OGTT or safety lab assessment
2. 2-h plasma glucose between 140 – 200 mg/dl (≥7.8 and <11.1 mmol/l) during OGTT

Patients not fulfilling all criteria on at least one visit are considered as patients without IGT finding

**TABLE 14.3-3.9 SUMMARY OF PATIENTS WITH LABORATORY PARAMETERS FULLFILING THE DEFINITION OF IMPAIRED FASTING GLUCOSE (IFG) (SAF)**

	Total	Number of patients with IFG (%)	Number of patients without IFG finding (%)
Female	XXX	XX (XX.X%)	XX (XX.X%)
Male	XXX	XX (XX.X%)	XX (XX.X%)
Total	XXX	XX (XX.X%)	XX (XX.X%)

IFG is defined as fulfilment of all of the following criteria:

1. FPG 110 - 125 mg/dl (6.1 - 6.9 mmol/l) during OGTT or safety lab assessment
2. 2-h plasma glucose < 140 mg/dl (<7.8 mmol/l) during OGTT

Patients not fulfilling all criteria on at least one visit are considered as patients without IFG finding.

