## 7.4 Safety

### 7.4.1 Carbohydrate metabolism

Fasting plasma glucose and insulin levels will be measured at baseline, at 6 and 12 months, then annually during GH treatment, and at the end of treatment.

After an overnight fast, venous blood samples will be taken to assess fasting glucose and insulin levels. Insulin resistance will be estimated using both the homeostasis model assessment (HOMA) (Matthews et al 1985) and quantitative insulin sensitivity check index (QUICKI) (Katz et al 2000, WHO 2002).

$$\text{HOMA} = \frac{\text{fasting insulin } (\mu\text{U/ml}) \times \text{fasting glucose } (\text{mg/dl})}{405 *}$$

\*use constant 22.5 instead of 405 if glucose concentration is reported in mmol/L

$$\text{QUICKI} = \frac{1}{\log \text{fasting insulin } (\mu\text{U/ml}) + \log \text{fasting glucose } (\text{mg/dl})}$$

Glycosylated haemoglobin (HbA1C) will be measured at baseline, at 6 and 12 months and then annually during GH treatment, and at the end of treatment.

An oral glucose tolerance test (OGTT) will be performed at baseline, at 6 and 12 months and then annually during GH treatment, and at the end of treatment.

The OGTT is a provocation test to examine the efficiency of the body to metabolise glucose. The OGTT provides information on latent diabetes states. The OGTT will be carried out according to WHO criteria (2002). After 3 days of an unrestricted, carbohydrate-rich diet, and after overnight fasting, 1.75 grams of glucose per kg body weight (up to a maximum of 75 g) will be administered orally after being dissolved in 250-300 ml of water. Blood samples will be taken 10 minutes before, and 120 minutes after the glucose load. Diabetes mellitus is defined by  $\geq 200$  mg/dl or  $\geq 11.1$  mmol/L blood glucose after 120 minutes.

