#### **Impaired Glucose Tolerance (IGT):**

FPG  $<$  126 mg/dl ( $<$ 7.0 mmol/l)

and

2-h plasma glucose between 140 – 200 mg/dl ( $\geq$ 7.8 and  $<$ 11.1 mmol/l)

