#### **Impaired Fasting Glucose (IFG):**

FPG 110 - 125 mg/dl (6.1 - 6.9 mmol/l)

and

2-h plasma glucose  $<$  140 mg/dl ( $<$ 7.8 mmol/l)

The identification of diabetes mellitus on laboratory results had to be in accordance to the documentation of diabetes mellitus as an AE.

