#### **4.6.2.2 Carbohydrate metabolism**

Fasting plasma glucose, insulin levels and glycosylated hemoglobin (HbA1C) are measured at baseline (start of treatment), at 6 and 12 months, then annually during GH treatment, and at the end of treatment. An OGTT is performed at the same time points.

The OGTT is a provocation test to examine the efficiency of the body to metabolize glucose. The OGTT provides information on latent diabetes states.

Insulin resistance will be estimated using both the homeostasis model assessment (HOMA) and quantitative insulin sensitivity check index (QUICKI)

$$\text{HOMA} = \frac{\text{fasting insulin } (\mu\text{U/ml}) \times \text{fasting glucose } (\text{mg/dl})}{405^*}$$

\*use constant 22.5 instead of 405 if glucose concentration is reported in mmol/L

$$\text{QUICKI} = \frac{1}{\log \text{fasting insulin } (\mu\text{U/ml}) + \log \text{fasting glucose } (\text{mg/dl})}$$

Carbohydrate metabolism data will be listed per parameter and will include: visit, sample date, parameter result, reference range, outside reference range indicator, clinical significance and a column containing comments.

Carbohydrate metabolism data as well as HOMA and QUICKI scores will be summarized by parameters and visit for the SAF for absolute values, and absolute and relative changes from baseline.

Shift tables for changes in the reference range classification as compared to baseline will be prepared for fasting plasma glucose, fasting insulin levels and HbA1C. The categories "low", "normal", "high" and "Missing" will be used in the shift tables. Shifts between categories will be displayed using absolute counts. Percentages will be provided per baseline category (without considering missings) for each post-baseline category, and based on all non-missing patients for total line/column.

In addition number and percentage of patients with DM and without DM finding will be presented. Patients fulfilling any criteria for DM given in section 4.5 will be regarded as patients with DM, patients not fulfilling any criteria on at least one visit will be considered as patients without DM finding.

Implausible insulin or glucose values will be excluded, i.e. Glucose values below 0.1 mmol/L and insulin values below 0.1 pmol/L will not be used for the calculation of HOMA and QUICKI.

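### With either fasting sample accepted and no precedence rule, one visit can count as DM and also as IFG or IGT

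*SAP*

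**What the plan says.** - **Definitions (SAP 4.5).** DM is met by any one of three limits: FPG of at least 126 mg/dl, a 2-h value of at least 200 mg/dl, or HbA1c of at least 6.5%. IGT needs FPG below 126 mg/dl and "2-h plasma glucose between 140 – 200 mg/dl". IFG needs "FPG 110 - 125 mg/dl (6.1 - 6.9 mmol/l", with a 2-h value below 140 mg/dl. No sample is named for FPG in any of the three.
- **IFG table (SAP Table 14.3-3.9, footnote).** The fasting condition is "FPG 110 - 125 mg/dl (6.1 - 6.9 mmol/l) during OGTT or safety lab assessment".
- **IGT table (SAP Table 14.3-3.8, footnote).** The fasting condition is "FPG < 126 mg/dl (<7.0 mmol/l) during OGTT or safety lab assessment".
- **DM table (SAP Table 14.3-3.7, footnote).** The fasting limit may be reached "during safety lab assessment or as -10min value of OGTT".
- **Sampling.** Protocol 7.4.1 schedules a fasting value: "Fasting plasma glucose and insulin levels will be measured at baseline, at 6 and 12 months, then annually during GH treatment". For the OGTT it adds: "Blood samples will be taken 10 minutes before, and 120 minutes after the glucose load". SAP 4.6.2.2 puts both at the same visits: "An OGTT is performed at the same time points".
- **Other rules.** Fasting-glucose retests are only listed (SAP 4.1). Each of the three tables counts a patient once if its criteria are met at one or more visits. No passage says what happens when the two fasting values disagree, or whether a DM visit can also count as IGT or IFG.

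**The concern.** For DM, the fasting limit is something to reach, and accepting either sample is the cautious choice. For IGT and IFG, the upper fasting limit is there to keep diabetic-range values out. Applied to a ceiling, an either-sample rule weakens it: the IGT fasting condition then fails only if every available fasting value is 126 mg/dl or more. A discordant visit therefore enters the DM table and an intermediate table together.

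SAP 4.5 sits under the analysis of the primary endpoint, and SAP 2.5 says that results will be compared with published data. Such a comparison needs a case definition that two programmers would code in the same way.

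**Working it through.** The documents give no figure on this point, so there is none to reproduce.

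**Step 1: are there two fasting values per visit?** Two are planned: the scheduled fasting plasma glucose and the OGTT pre-load sample. SAP 5.5 lists Glucose (16.2.6.2) and OGTT (16.2.6.4) separately, and the DM footnote treats them as two sources. The documents do not say whether they come from one draw or two.

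**Step 2: worked visits (mmol/l, representative values).**

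| Safety lab | OGTT -10 min | 2-h | HbA1c | Classes met |
|---|---|---|---|---|
| 7.2 | 6.5 | 6.0 | 5.3% | DM and IFG |
| 7.2 | 5.0 | 9.0 | 5.3% | DM and IGT |
| 6.5 (single FPG) | – | 6.0 | 6.6% | DM and IFG |
| 5.0 (single FPG) | – | 9.0 | 6.6% | DM and IGT |

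The first two rows need the either-sample rule. The last two do not; they follow from SAP 4.5 alone.

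**Step 3: all category combinations.** Take three fasting classes (below 6.1, 6.1–6.9, 7.0 or more), three 2-h classes and two HbA1c classes.
- Single FPG: 3 × 3 × 2 = 18 combinations. Three are DM plus IFG or IGT (1 IFG, 2 IGT), all through HbA1c of 6.5% or more.
- Either sample: 3 × 3 × 3 × 2 = 54 combinations. Nineteen overlap. Thirteen have HbA1c of 6.5% or more; the other 6 (2 IFG, 4 IGT) arise only from discordant fasting values.
- Naming one FPG removes the 6 but leaves 3 of 18. Excluding DM visits from IGT and IFG removes all of them.

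**Step 4: direction for IFG.** Let A and B be the events that each fasting value lies in 6.1–6.9. Then P(A or B) = P(A) + P(B) − P(A and B), which is never below P(A). If the two values are equally likely to lie in the band, the ratio to one sample is 2 − P(A and B)/P(A). That is 1 if they are identical and at most 2.

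**Step 5: illustration of size.** All inputs are assumed, none is in the documents: mean fasting glucose 4.8–5.2 mmol/l, between-child SD 0.5, independent SD per value 0–0.4, rounding to one decimal. The 2-h condition is not applied.

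| Mean | SD per value | Band, one sample | Band, either | Ratio | DM plus IFG band via FPG, per 1000 visits |
|---|---|---|---|---|---|
| 4.8 | 0 | 0.62% | 0.62% | 1.00 | 0 |
| 4.8 | 0.1 | 0.71% | 0.92% | 1.30 | 0.01 |
| 4.8 | 0.4 | 2.50% | 4.42% | 1.77 | 0.43 |
| 5.2 | 0.1 | 4.75% | 5.84% | 1.23 | 0.24 |
| 5.2 | 0.4 | 8.93% | 14.70% | 1.65 | 3.79 |

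**Step 6: IGT.** The share of visits with FPG below 7.0 moves at most from 99.68% to 99.96%, or 0.28 percentage points. The 2-h value decides IGT, so the count barely changes.

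**The case against.** The other side has a good case on several points.

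- **The footnotes do not contradict SAP 4.5.** A reader might infer that 4.5 fixes one FPG and that the tables depart from it. It names no sample; the footnotes fill a gap. This stands.
- **Exclusivity was never promised.** The three tables are separate patient-level counts, and a child with IFG in one year and DM in a later year belongs in both. SAP 4.5 already permits same-visit overlap through HbA1c. This stands too, so the either-sample rule is only one of two routes.
- **Either-sample is a defensible, sensitive rule in a single-arm safety study.** Ranking the -10-min value first would lower a safety count, and no passage supports that ranking. This stands against making it the main analysis, but not against showing it as a sensitivity count.
- **Discordant values can be found in the listings.** They can, but a listing does not decide how the tables count them.
- **IGT and IFG are not named as endpoints in SAP 2.3, and the published on-treatment figures quoted in Protocol 1.2.4 are for IGT.** This limits the importance. It does not explain why a visit with a diabetic-range fasting value should also be tabulated as impaired fasting glucose.

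**Conclusion.** The point holds as a gap in classification. On the stated rules, a visit with fasting values of 7.2 and 6.5 mmol/l and a normal 2-h value is DM and IFG at once, although SAP 4.5 puts a ceiling on the IFG fasting value. The FPG route requires the two values to be separate draws that disagree across 126 mg/dl; the HbA1c route does not.

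A reader might infer that IFG is over-counted by a known factor. The documents do not support that. The rule can only raise IFG relative to one named sample, but no reference sample is named. The rise is nil if both values come from one draw, and the 1.23- to 1.77-fold range rests wholly on assumed variability without the 2-h condition. Nor do the documents support a claim that IGT is inflated, since its count hardly moves. The DM count is not affected.

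**What to change.** 1. In SAP 4.5 and the footnotes to Tables 14.3-3.8 and 14.3-3.9, state that a visit meeting any DM criterion (either fasting sample, 2-h value or HbA1c) is not counted as IGT or IFG at that visit. Findings at other visits still count.
2. Keep the either-sample rule for DM in Table 14.3-3.7.
3. Add a sensitivity row for IFG that uses only the OGTT -10-min value paired with the 2-h value of the same test, and the safety-laboratory value if the -10-min value is missing. This shows how far the IFG count depends on the choice of sample.

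The cost is a sentence of SAP text, matching footnotes, a small programming change and one extra table row. The downside is slightly fewer IFG and IGT cases. The excluded visits still appear under DM and in the HbA1c, glucose and OGTT listings.
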